5.1.1. End of Study Definition

The end of study for this study is defined as the last visit of the last patient.

5.2. Planned Interim Analysis

Interim analyses may be conducted during the course of the study by the unblinded team to assess efficacy, safety, and futility. If the timing of this analysis falls within a few weeks of the first-step analysis, only the first-step analysis will be performed. Enrollment (up to a maximum of approximately 50 patients) may be halted if the incidence of pancreatitis is much lower than anticipated, making the evaluation of a treatment effect on pancreatitis futile. Details of the interim analysis will be provided in the SAP.

5.3. Study Committees

5.3.1. Independent Data Monitoring Committee

An Independent Data Monitoring Committee (IDMC), composed of members who are independent from the sponsor and the study investigators, will monitor patient safety by conducting formal reviews of accumulated safety data that will be blinded by treatment group; if requested, the IDMC may have access to the treatment allocation code or any other requested data for the purposes of a risk-benefit assessment.

The IDMC will provide the sponsor with appropriate recommendations on the conduct of the clinical study to ensure the protection and safety of the patients enrolled in the study. The IDMC will also institute any measures that may be required for ensuring the integrity of the study results during the study execution.

All activities and responsibilities of the IDMC are described in the IDMC charter.

6. SELECTION, WITHDRAWAL, AND REPLACEMENT OF PATIENTS

6.1. Number of Patients Planned

The study will enroll up to approximately 50 patients at approximately 20 study sites globally.

6.2. Study Population

The study population will be males and females ≥ 18 to 75 years of age with a history of fasting TG ≥ 1000 mg/dL, a fasting TG ≥ 500 mg/dL during screening, and a history of pancreatitis. The study will enroll up to approximately 50 adult male and female patients at approximately 20 sites globally. Efforts will be made to select sites with a large population of well-characterized patients who have previously undergone gene sequencing and other procedures to understand the etiology of the HTG.

The following LPL pathway cohorts will be enrolled based upon the patient's genotype:

1. Cohort 1: FCS due to complete LPL deficiency. Approximately 6 to 9 patients will be enrolled. This cohort consists of patients:
 - With known homozygous or compound heterozygous null LPL, GPIHBP1, or APOC2 LOF mutations
2. Cohort 2: Multifactorial chylomicronemia with partial LPL deficiency. Approximately 9 to 12 patients will be enrolled. This cohort consists of patients:
 - with known heterozygous null LPL, GPIHBP1, or APOC2 LOF mutations, or
 - with uncharacterized or known non-null LOF LPL pathway gene mutations (LPL, APOC2, APOA5, LMF1 and GPIHBP1)
3. Cohort 3: Multifactorial chylomicronemia. Approximately 15 to 27 patients will be enrolled. This cohort consists of patients not included in cohorts 1 or 2 above:
 - with other monogenic or polygenic causes of sHTG (eg, CGKR, CREB3L3, E2/E2 dysbetalipoproteinemia), or
 - without genotype information

6.2.1. Inclusion Criteria

A patient must meet the following criteria to be eligible for inclusion in the study:

1. Males and females ≥ 18 to 75 years of age at screening
2. Previous documentation in the patient's medical records of a fasting serum TG measurement ≥ 1000 mg/dL (11.3 mmol/L) on more than 1 occasion, and all fasting TG values ≥ 500 mg/dL (5.6 mmol/L) at screening

NOTE: TGs will be measured at least twice and at least 4 days apart during the screening period.

3. History of a hospitalization and diagnosis of acute pancreatitis in the past 10 years. (Sponsor may elect to drop the time specification if sufficient enrollment does not occur within a reasonable period of time).
4. On a stable lipid-modifying diet with or without medications (eg, statins, niacin, omega-3 fatty acids). Lipid-modifying diet and doses of medications should be stable for at least 4 weeks (6 weeks for fibrates, 8 weeks for PCSK9 inhibitors) prior to screening
5. BMI index of 18-40 kg/m²
6. Willing to consume no more than an average of 2 standard alcoholic drinks per day and a maximum of 15 standard alcoholic drinks per week for the duration of the study. (A standard alcoholic drink is the equivalent of 12 ounces (355 mL) of beer, 5 ounces (148 mL) of wine, or 1.5 ounces (44 mL) of hard liquor)
7. Willing to refrain from consumption of alcohol for 24 hours prior to each study visit
8. Willing to refrain from cigarette smoking for 24 hours prior to each study visit
9. Willing to consistently maintain previously recommended diet and exercise regimen for duration of the study
10. Willing and able to comply with clinic visits and study-related procedures
11. Provide signed informed consent
12. Able to understand and complete study-related questionnaires

6.2.2. Exclusion Criteria

A patient who meets any of the following criteria will be excluded from the study:

1. A hospital or clinic discharge diagnosis of acute pancreatitis within 12 weeks of screening
2. Lipid apheresis or plasma exchange treatment within the last 4 weeks or plans to undergo apheresis or plasma exchange during the time frame of the study
3. History of class 3/4 heart failure at any time in the past, or hospitalization for heart failure, diagnosis of a myocardial infarction, stroke, TIA, unstable angina, CABG, PCI, carotid surgery/stenting within 3 months before the screening visit
4. History of bleeding disorders, esophageal varices, heparin induced thrombocytopenia, or contraindications to receiving heparin (eg, allergic reaction to heparin)
5. New clinically significant findings on 12-lead electrocardiogram (ECG) that would place the patient at risk or interfere with participation in the study
6. Dose(s) of any permitted concomitant medications that have changed in the time period prior to screening as described in Section 7.8.2
7. Presence of any clinically significant uncontrolled endocrine disease known to influence serum lipids or lipoproteins

NOTE: Patients on thyroid replacement therapy are eligible if the dosage of thyroxine has been stable for at least 12 weeks prior to screening visit

8. Use of systemic corticosteroids, unless used as replacement therapy for pituitary/adrenal disease (in which case must be a stable regimen for at least 6 weeks prior to the screening visit)
NOTE: Topical, intra-articular, nasal, inhaled and ophthalmic steroid therapies are not considered as 'systemic' and are allowed
9. Calculated eGFR <45 ml/min (according to 4-variable MDRD study equation)
10. History of drug or alcohol abuse (including binge drinking which typically involves consumption of approximately 4 drinks for women and 5 drinks for men in a few hours) within 1 year of screening
11. Exposure to another investigational drug or therapy within 30 days or within at least 5 half-lives (whichever is longer) prior to the screening visit
12. Blood donation of any volume within 1 month prior to administration of study drug
13. Known hypersensitivity to monoclonal antibody therapeutics. Known sensitivity to any of the components of the investigational product formulation
14. History of malignancy within 5 years prior to screening (other than successfully treated nonmetastatic cutaneous squamous cell or basal cell carcinoma and or localized carcinoma in situ of the cervix)
15. Any medical or psychiatric condition that, in the opinion of the investigator, would place patient at risk, interfere with participation in the study or interfere with the interpretation of the study results (eg, cirrhosis or chronic active hepatitis, nephrotic syndrome, uncontrolled diabetes, uncontrolled hypertension)
16. Previous treatment with Glybera® in the past 5 years or treatment with lomitapide or mipomersen in the past 6 months
17. Positive serum hCG pregnancy test at the screening visit
18. Creatine phosphokinase (CPK) $\geq 3x$ upper limit of normal (ULN) at the screening visit
19. Aspartate aminotransferase (AST) or alanine aminotransferase (ALT) $\geq 3x$ ULN
20. Thyroid-stimulating hormone (TSH) >1.5 ULN or $<$ lower limit of normal
21. Platelet count $<75,000$
22. Any patient who is the investigator or any sub-investigator, research assistant, study coordinator, or other staff directly involved in the conduct of the protocol, or a family member of staff involved in the conduct of the protocol
23. Pregnant or breast feeding women
24. Women of childbearing potential (WOCBP)* who are unwilling to practice a highly effective birth control method prior to the initial dose, during the study, and for 24 weeks after the last dose of study drug. Highly effective contraceptive measures include:
 - Stable use of combined (estrogen and progestogen containing) hormonal contraception associated with inhibition of ovulation initiated 2 or more menstrual cycles prior to screening:

- oral
- intravaginal
- transdermal
- Stable use of progestogen-only hormonal contraception associated with inhibition of ovulation initiated 2 or more menstrual cycles prior to screening:
 - oral
 - injectable
 - implantable
- intrauterine device (IUD)
- intrauterine hormone-releasing system (IUS)
- bilateral tubal ligation
- Vasectomized partner. Note: Vasectomized partner is a highly effective birth control method provided that the partner is the sole sexual partner of the woman of child bearing potential trial participant and that the vasectomized partner has received medical assessment of the surgical success
- Sexual abstinence. Note: Sexual abstinence is considered a highly effective method only if defined as refraining from heterosexual intercourse during the entire period of risk associated with study treatments.

*Postmenopausal women must be amenorrheic for at least 12 months in order **not** to be considered of childbearing potential. Postmenopausal status will be confirmed by measurement of follicle-stimulating hormone (FSH). Pregnancy testing and contraception are not required for women with documented hysterectomy and/or oophorectomy.

25. Men who are sexually active with WOCBP and are unwilling to consistently use condoms during the study drug treatment period and for 24 weeks after the last injection of study drug, regardless of vasectomy status. Sperm donation is prohibited during the study and for up to 24 weeks after the last injection of study drug.

6.3. Premature Withdrawal from the Study

A patient has the right to withdraw from the study at any time, for any reason, and without repercussion.

The investigator and/or sponsor have the right to withdraw a patient from the study if it is no longer in the interest of the patient to continue in the study, or if the patient's continuation in the study places the scientific outcome of the study at risk (eg, if a patient does not or cannot follow study procedures). An excessive rate of withdrawals would render the study uninterpretable; therefore, unnecessary withdrawal of patients should be avoided. The site will be provided a retention manual outlining the best practices for patient retention.

Patients who are withdrawn prematurely from the study will be asked to complete study assessments, as described in Section 8.1.2.

Rules for discontinuation of study treatment (permanent or temporary) are discussed in Section 7.4.2.

6.4. Replacement of Patients

Patients prematurely discontinued from the study/ study drug will not be replaced.

7. STUDY TREATMENTS

7.1. Investigational and Reference Treatments

Sterile evinacumab drug product will be provided in a 20 mL single-use glass vial at a concentration of 150 mg/mL.

Double-Blind Treatment Period: Patients will be randomized to receive either evinacumab 15 mg/kg or matching placebo administered IV every 4 weeks (± 4 days) on days 1, 29, and 57.

Single-Blind Treatment Period: All patients will receive evinacumab administered IV at a dose of 15 mg/kg every 4 weeks (± 4 days) on days 85, 113, and 141.

Instructions on management of infusion reactions are provided in Section 7.5.

Instructions on dose preparation are provided in the pharmacy manual.

7.2. Run-in Treatment(s)

On day -28, all patients will receive an IV placebo infusion. Placebo will be supplied in vials that match evinacumab, but do not contain the protein.

7.3. Pretreatment(s)

After confirmation of eligibility, patients will receive an IV bolus of 60 IU of heparin per kg of body weight at screening visit 2.

7.4. Dose Modification and Study Treatment Discontinuation Rules

7.4.1. Dose Modification

Dose modification for an individual patient is not allowed.

7.4.2. Study Drug Discontinuation

Patients who permanently discontinue from study drug before entering the double-blind treatment period (day 1, week 0) will be contacted to assess any adverse events (AEs) but will not be asked to return for the remaining study visits.

Patients who permanently discontinue from study drug during the double-blind treatment period will be asked to return to the clinic within 5 days for an early termination visit consisting of week 12 study assessments; these patients will then enter the off-drug treatment follow-up period.

Patients who are permanently withdrawn from study drug during the single-blind treatment period will be asked to return to the clinic for an early termination visit consisting of week 24 study

assessments. After the early termination visit, patients will enter the off-drug treatment follow-up period.

Patients who are unable or unwilling to attend the study visits as described above should still be followed for at least 24 weeks from the last dose of study drug or up to recovery or stabilization of any AE to be followed-up as specified in this protocol, whichever comes last. The assessments completed should include pregnancy testing for WOCBP. A final end of study visit should take place with assessments as specified in the end of study visit (ie, follow up visit) at 24 weeks after the premature discontinuation of study drug.

Sexually active males and WOCBP who discontinue the study prematurely should be reminded at the early termination visit following treatment discontinuation to maintain the contraceptive measures (as described in Section 6.2.2) for 24 weeks after the last dose of study drug. At this visit, WOCBP will be provided a sufficient number of urine pregnancy tests with instructions to test for pregnancy 4 weeks after this visit and every 4 weeks (Q4W) thereafter. The patient will also be notified of Q4W follow-up phone calls to confirm continued contraception use, to obtain results of urine pregnancy tests, and to obtain information on whether pregnancy has occurred in WOCBP and in female partners of male patients.

The investigator should make the best effort to contact any patient (eg, contacting patient's family or private physician, review available registries or health care database) who fails to return to the site, and to determine health status. Attempts to contact such patients must be documented in the patient's records (eg, times and dates of attempted telephone contact, receipt for sending a registered letter).

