Elevated blood levels of TGs have been associated with the development of both CVD and acute pancreatitis. Current therapies for lowering TGs (eg, weight reduction, lifestyle changes, statins, fibrates, omega-3 fatty acids) have limited efficacy and/or tolerability issues. Recent studies have demonstrated that patients with genetic LOF mutations that decrease the activity of LPL can result in severe elevations in TG. Because ANGPTL3 acts as a natural inhibitor of LPL, blockade of ANGPTL3 and preventing LPL inhibition is a potential target for the treatment of elevated levels of TGs. Importantly, no identified safety risks from the absence of ANGPTL3 have been reported for the few individuals who are homozygous for LOF mutations in ANGPTL3 ([Musunuru 2010](#), [Minicocci 2012](#)). In fact, recent studies have demonstrated that genetic LOF variants which result in lower TG levels (eg, APOC3, ANGPTL3, and ANGPTL4 LOF genetic variants) are associated with a decreased risk of myocardial infarction ([Musunuru 2010](#), [Stitzel 2016](#), [Dewey 2016](#), [Crosby 2014](#), [Dewey 2017](#)). A therapeutic targeted to ANGPTL3 could provide beneficial changes in the lipid profile and ultimately in the cardiovascular (CV) risk for patients. Additionally, significant reductions in TGs would also benefit the patient with severe elevations in TGs at risk for pancreatitis. Thus, a significant unmet need exists for additional and improved methods for treating elevated TG levels.

Evinacumab has been evaluated in 3 clinical studies and has been generally well tolerated with no significant clinical safety findings observed to date. No important identified risks have been established. The important potential risks with evinacumab (based on preclinical evaluation, mechanism of action, or risks associated with monoclonal antibody [mAbs] in general) include systemic hypersensitivity reactions, immunogenicity, and embryofetal toxicity. For the potential embryofetal toxicity risk, there is a strict risk mitigation plan, including requirements for consistent use of contraception for sexually active male study participants and sexually active female study participants of child-bearing potential. Currently, the available safety data along with the risk minimization and management activities for all important potential risks support the continued development of this compound.

Population:

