7.4.2.1. Reasons for Permanent Discontinuation of Study Drug

Study drug dosing will be permanently stopped in the event of:

- Evidence of pregnancy
- Acute systemic injection reactions with AEs including, but not limited to, anaphylaxis, laryngeal/pharyngeal edema, severe bronchospasm, chest pain, seizure or severe hypotension
- Withdrawal of patient consent

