8.1.1. Footnotes for the Schedule of Events Table

1. Patients who are permanently withdrawn from study drug before entering the double-blind treatment period (day 1, week 0) will be contacted to assess any AEs.
2. Patients who are permanently withdrawn from the study drug during double-blind period will be asked to return to the clinic for an early termination visit consisting of week 12 study assessments. After the early termination visit, patients will enter the off-drug treatment follow-up period.
3. Patients who are permanently withdrawn from study drug during the single-blind treatment period will be asked to return to the clinic for an early termination visit consisting of week 24 study assessments. After the early termination visit, patients will enter the off-drug treatment follow-up period.
4. Visit 1b must occur at least 4 days after visit 1.
5. Patients will undergo end of double-blind treatment period assessments at the week 12 visit, which is the first visit of administration of single-blind evinacumab.
6. Medical history should include detailed cardiovascular and pancreatitis history.
7. The patient should be fasting for at least 8 hours prior to the post-heparin procedure for measurement of LPL activity. The patient should not consume any alcohol 48 hours prior to the post-heparin plasma blood draw. Heparin (60 U/kg body weight) should be administered IV by bolus injection. Venous blood should be collected 10 minutes after the bolus injection. Prior to discharge from the clinic, patients should then be observed for 1 hour post-heparin administration for any AEs.
8. Following the screening period and confirmation of eligibility, patients will receive an IV bolus of 60 IU of heparin per kg of body weight at visit 2.
9. At dosing visits, all assessments (including urine or serum pregnancy tests for WOCBP) should be performed and all blood samples should be collected before the dose of study drug is administered.
10. Vital signs should also be measured and AEs monitored pre-dose, at the end of study drug infusion, between 30 to 60 minutes post dose, and at approximately 120 minutes post dose. Patients will be closely monitored for a minimum of 120 minutes after IV administration of study drug.
11. Patients should fast for a minimum of 8 hours prior to all blood draws. For patients with diabetes, investigators may hold a patient's morning diabetes medications until labs are drawn and the patient has eaten.

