12. Lipids and lipoproteins, total cholesterol, LDL-C, HDL-C, TG, APOB, APOA1, and Lp(a) will be measured except at visit 1 and 1b.
13. At visit 1 and visit 1b, only total cholesterol, LDL-C, HDL-C, and TG will be measured.
14. Lipoprotein lipase level enzyme activity will be measured in fasting plasma collected at visit 2 only after eligibility has been confirmed by screening procedures at visit 1 and visit 1b.

15. Questionnaires should be completed daily for 7 days prior to each visit except for visit 3 (to be completed daily for the duration between visit 2 and visit 3).
16. Patients should be reminded by phone call 1 week prior to their visit to complete questionnaires.
17. Electrocardiogram should be performed before blood is drawn during visits that require blood draws.
18. In addition to assessment of adverse events at each visit, investigators should also ask patients if they have had any changes in abdominal symptoms and/or medical clinic visits for abdominal symptoms.
19. Confirm required contraception use and pregnancy status of female patients of childbearing potential and female partners (of child-bearing potential) of male patients will be monitored at clinic visits and by phone call for 24 weeks post the last dose of study drug. Women of childbearing potential will be provided urine pregnancy tests with instructions to test for pregnancy on days corresponding to phone call visits or Q4W if patients do not attend regularly scheduled visits.
20. Imaging may be performed up to 1 week prior to the visit and may be on the same day of the visit (for visit 3, MRI can be done on the same day or up to 4 days after visit 3). If done on the day of the visit, vital signs, ECG and blood draws after an 8-hour fast should be completed prior to the imaging procedures. Imaging procedures should be performed prior to study drug infusion.
21. PK samples will also be used for the analysis of total ANGPTL3.
22. In addition to the PK sample collected prior to drug administration, a PK sample should be obtained immediately after the end of each infusion.

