Figure 2: ^{18}F -FDG PET showing decrease of signal in areas of AIP inflammation (pancreas, salivary glands and retroperitoneum) after up to 2 months of prednisolone treatment (0.5 mg/kg, baseline on the left, post-treatment on the right) (Lee 2009).

^{18}F -FDG PET has been shown to be able detect inflamed/vulnerable atherosclerotic plaque in the carotid of patients (Figure 3) (Tawakol 2006) and to detect ~15% reductions in signal following 12 weeks of treatment with high-dose statin (versus low dose statin) in N=34 patients (Tawakol 2013). Since the acquisitions with ^{18}F -FDG PET in the present study will include the neck and thoracic regions, it will be possible to assess suspect areas of atherosclerotic plaque in the carotid and aorta of patients. Reduction of signal (target to background ratio - TBR) in these areas would indicate a potential beneficial effect of ANGPTL3 inhibition on atherosclerotic lesions. ANGPTL3 inhibition in rodents has led to reductions in atherosclerotic plaque. Since ^{18}F -FDG-PET can detect inflammation in atherosclerotic lesions, we plan to explore imaging of the carotids and aorta before and after treatment, without any further isotope dosing or radiation exposure.

Figure 3: Axial CT and co-registered PET images from 2 patients. Patient A showed low ¹⁸F-FDG uptake in the region of the carotid plaque, while Patient B had high uptake in the region of the carotid plaque. The uptake difference was consistent with high inflammatory infiltration in the atherosclerotic plaque of patient B compared to patient A as determined from excised tissue samples.

¹⁸F-FDG PET scans (including a low-dose CT scan) result in typical effective radiation doses of 7 to 10 mSv per study for an adult (19 microSv/MBq) (ICRP 80). The maximum recommended allowed effective dose for a research patient in a single year is 50 mSv (21CFR361.1). Two ¹⁸F-FDG PET studies would result in an approximate dose of 20 mSv, or 40% of the recommended maximum allowed dose. Risk and management of radiation exposure will be disclosed to patients in the informed consent form. ¹⁸F-FDG PET will be performed at week 2 and at week 16 (12 weeks after initiation of evinacumab treatment).

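### The double-blind early termination visit brings in the week 12 FDG-PET/CT with no exception for a patient stopped for pregnancy, and the order of pregnancy test and scan is not fixed

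*Protocol*

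**What the plan says.** The first entry among the reasons for permanent discontinuation in Protocol 7.4.2.1 is "Evidence of pregnancy". What follows a permanent stop depends on the period (Protocol 7.4.2):

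- Before day 1, the patient is only contacted about adverse events.
- In the double-blind period, the patient is asked to "return to the clinic within 5 days for an early termination visit consisting of week 12 study assessments".
- In the single-blind period, the visit consists of week 24 assessments instead.

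The double-blind rule recurs in footnote 2 to Table 1, where patients are to be "asked to return to the clinic for an early termination visit consisting of week 12 study assessments", and in 8.1.2, which refers to Table 1 for the content. The SAP copies footnote 2 in its section 10.4.1.

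Table 1 marks FDG-PET at visit 4 and at visit 10 (week 12). Section 10.4.3.2 confirms the two time points as week -2 and week 12. Section 8.2.4.1 says that the scans include a low-dose CT and "result in typical effective radiation doses of 7 to 10 mSv per study for an adult".

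On timing, footnote 20 says: "Imaging may be performed up to 1 week prior to the visit". It also allows imaging on the visit day, in which case vital signs, ECG and fasting blood draws come first. Footnote 9 says that at dosing visits the assessments, pregnancy tests included, precede study drug. The visit 10 pregnancy test is a urine test.

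**The concern.** The stopping rule and the early termination rule do not refer to each other. The first foresees pregnancy. The second fixes the content of the next visit without regard to why the patient stopped, and that content includes a research scan with ionising radiation. Section 7.4.2 even gives contraception reminders and urine test kits to women of childbearing potential at this visit, but does not say how the visit changes for a woman already known to be pregnant.

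The scheduled scans raise a related point. A pregnancy test is placed at the week 12 visit, but nothing places it before the PET, and the imaging window lets the scan come first.

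What is at stake is participant safety, not the primary analysis.

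**Working it through.** No power or alpha calculation is involved. The check consists of tracing the rule, reproducing the one nearby figure, and day arithmetic.

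**1. Tracing the rule**

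| Step | Place | Content | Exception for pregnancy? |
|---|---|---|---|
| Stop | 7.4.2.1 | Pregnancy permanently stops study drug | – |
| Visit | 7.4.2 | Week 12 assessments, within 5 days | None |
| Visit | 8.1.2 | Week 12 assessments as in Table 1 | None |
| Visit | Footnote 2 | Week 12 assessments, no 5-day limit | None |
| Content | Table 1, visit 10; 10.4.3.2 | FDG-PET at week 12 | None |
| Scan | 8.2.4.1 | Low-dose CT included | None |

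The omission is in all three statements of the rule. The PET routing is confined to double-blind stops, because visit 13 (week 24) has MRI but no PET.

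**2. Dose, reproducing the protocol's figure**

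Section 8.2.4.1 gives about 20 mSv for two scans, or 40% of a 50 mSv annual maximum.

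- Upper end: 2 × 10 = 20 mSv; 20/50 = 40%. This reproduces the stated figures.
- Lower end: 2 × 7 = 14 mSv; 14/50 = 28%.

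One scan at an early termination visit is therefore 7 to 10 mSv. This is effective dose to an adult. The documents give no fetal dose.

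**3. Last pregnancy test to week 12 PET, scan done before the visit**

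Inputs: visit 9 on day 57 ± 4 (urine test), visit 10 on day 85 ± 4, scan up to 7 days before visit 10.

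- Nominal scan days: 85 − 7 = 78 to 85 − 1 = 84.
- Nominal interval: 78 − 57 = 21 to 84 − 57 = 27 days.
- Longest with windows: visit 10 on day 89, scan on day 88, visit 9 on day 53; 88 − 53 = 35 days.
- Shortest with windows: visit 10 on day 81, scan on day 74, visit 9 on day 61; 74 − 61 = 13 days.

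For a scan on the visit day but ahead of the test, the interval is nominally 85 − 57 = 28 days, and at most 89 − 53 = 36.

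**4. Which footnote would put the test first?**

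Footnote 20 names vital signs, ECG and blood draws. A urine test is none of these. Footnote 9 orders the test before the dose and does not mention imaging. It also speaks only of dosing visits, so it does not govern an early termination visit, where no dose is given.

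**5. Baseline PET (visit 4)**

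In the protocol's Table 1 as extracted, the pregnancy test row is blank at visit 4. The previous test is then at visit 3 (day -28). For a scan on the visit day the interval is nominally −14 − (−28) = 14 days, and at most −10 − (−28) = 18 days. A scan a week before the visit gives nominally −21 − (−28) = 7 days.

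The SAP's copy of the row, as extracted, shows a urine test at visit 4. That copy leaves visits 5 and 7 blank, although both are dosing visits at which footnote 9 expects a test, so its columns may have shifted. Some rows of the protocol's table also appear shifted. This item therefore needs confirming against the original table.

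**The case against.** The best case against the point is that other safeguards would stop the scan:

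- Pregnancy is reportable to the sponsor within 24 hours and is an event of special interest (9.4.3).
- The medical monitor is to be contacted about any discontinuation (7.4.2.2).
- Safety monitoring follows GCP (9.6).
- Patients are asked, not obliged, to attend, and 7.4.2 provides for those who do not.
- The stopping reasons also include withdrawal of consent, so the early termination text is plainly generic.
- Section 8.2.4.1 leaves disclosure of radiation risk and its management to the consent form, which is not among the documents available here.
- Highly effective contraception is required (6.2.2) and confirmed at each visit. The nominal 21 to 27 days lies within the study's four-weekly dosing and testing cycle; only the window extremes go beyond 28.

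Much of this stands. It makes an actual exposure unlikely and keeps the number of patients small. It does not alter the written instruction, which has no exemption. A consent form that discloses the risk does not change what 7.4.2 tells the site to do.

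Two stronger readings are tempting and should not be adopted.

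First, a reader might infer that the protocol contradicts its own safety plan, since 3.2.1 says: "For the potential embryofetal toxicity risk, there is a strict risk mitigation plan". That plan concerns the potential risk of evinacumab, and the measure it names is contraception. It does not mention imaging or radiation, so no contradiction with it is shown.

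Second, a reader might see the same fault in the heparin bolus, because a single-blind stop leads to "an early termination visit consisting of week 24 study assessments" and the week 24 column includes heparin. The bolus is scheduled for every patient who reaches that visit, so any lack of re-checking against the heparin exclusion is not caused by the early termination rule. No passage lists pregnancy as a heparin contraindication.

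**Conclusion.** The point holds as an unreconciled gap between the pregnancy stopping rule, the early termination visit and the imaging footnote. Followed literally, the text schedules an FDG-PET/CT of 7 to 10 mSv (adult effective dose) for a patient stopped for pregnancy in the double-blind period. It also allows the scheduled week 12 PET before that visit's pregnancy test, nominally 21 to 27 days after the previous one and up to 35 with windows.

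The conclusion assumes that the visit 10 column of Table 1 defines the early termination visit, as 8.1.2 says, and that no document outside this set overrides it. The consent form and any imaging manual could not be checked. The baseline-scan gap is provisional because the two copies of the table differ.

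It does not follow that a pregnant patient would in practice be scanned, that single-blind stops are affected, or that a particular fetal dose can be stated. The triglyceride analysis is unaffected. The matter is worth fixing because it concerns participant safety and takes only a few sentences to settle.

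**What to change.** The sponsor should make two reconciliations and one check, setting the clinical rule itself:

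1. Reconcile 7.4.2, 8.1.2 and footnote 2 with 7.4.2.1, so that the text states which week 12 assessments apply at an early termination visit when the reason for stopping is pregnancy. The 5-day limit, present in 7.4.2 but absent from 8.1.2 and footnote 2, can be aligned in the same edit.
2. Reconcile footnotes 9 and 20, so that the order of pregnancy testing and FDG-PET is stated and consistent, both on the visit day and when the scan is done ahead of the visit.
3. Confirm from the original Table 1 whether visit 4 carries a pregnancy test, and align the SAP copy. The sentence in 8.2.4.1 that places PET at weeks 2 and 16 also needs reconciling with week -2 and week 12 in 10.4.3.2.

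The cost is a short protocol amendment, with the SAP's copied footnotes updated to match. Depending on the rule chosen, a few week 12 PET values may be missing. Since SAP 3.7 requires a baseline and a post-baseline PET, those patients would leave the PET analysis set.
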